12.4.2 Intention-to-treat Population

This set contains all randomized subjects.

12.4.3 Per Protocol Population

	Study Title	Bioavailability Study of COQUN ORAL FORMULATION (CoQ10) administered in Healthy Adults (CoQ10-01)		
	Study ID	VF-BAQ10/2018	Sponsor:	VISUFARMA SpA
	Date	March 03, 2018	Vers.	Final

The per protocol population consists of all subjects who meet all inclusion/exclusion criteria and who do not have any major protocol deviation.

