3.3 Data Review

No data review has been planned in this study.

	Form	Form No.	1M-DMST-011-01-A1
	Statistical Analysis Plan	Page	Page 10 of 69
		Effective Date	07/05/2018

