5. STATISTICAL ANALYSIS: DEFINITIONS, DERIVATIONS, CALCULATIONS AND METHODOLOGY

5.1 Baseline Characteristics

5.1.1 Disposition of Subjects

Collected Variables:

- Treatment group assigned (categories: treatment 1/treatment 2) [CRF – Visit 2]
- Has the subject completed the study (yes, no) [CRF - EOS]
- Primary reason for the premature termination (free text) [CRF - EOS]
- Date of informed consent [CRF – Visit 1]
- Is the subject eligible for entering the study (yes, no) [CRF – Visit 1]
- Inclusion/exclusion criteria (yes, no) [CRF – Visit 1]
- Was the investigational product taken correctly? (yes, no) [CRF – Visit 3, 4, 5]

Derived Variables:

- whether the subject belongs to the :
 - safety set (subjects must have signed the informed consent and they must have taken at least one dose i.e. the answer to the question "Was the investigational product taken correctly" must be "yes" at least once)
 - ITT set (subjects must have been randomized)
 - PP set (subjects must have been randomized and they do not have major deviations)

Imputations for missing values:

If the date of last intake of study medication is not available, due to premature termination or other reasons, date of last investigational product intake (collected in the end of study form of the CRF) will be imputed.

Analysis Sets to be used for:	Tables	Table1: All subjects
	Listings	Tables 2,3, 4: ITT analysis set Listing 1: All subjects Listings 2, 3, 4: ITT analysis set
	Figures	Figure 1: All subjects Figure 2: ITT analysis set

Subject disposition will be summarized by treatment group as follows:

Table 1. Number of Subjects and Subjects Disposition (Total set)	Total number of subjects screened, randomized and number of subjects in analysis sets will be presented by treatment group. The percentage of subjects will be calculated relative to the number of all randomized subjects.
---	---

Table 2. Reasons for premature study termination (All Randomized Subjects)	For study termination and for premature discontinuation reason, a default frequency tabulation will be provided. The percentage of subjects will be calculated relative to the number of subjects who were randomized.
---	---

Table 3. Analysis Sets (All Randomized Subjects)	Subject analyses set status will be summarized for each treatment group, together with the reason(s) for exclusion from the Safety, ITT and PP
---	--

	Form	Form No.	1M-DMST-011-01-A1
	Statistical Analysis Plan	Page	Page 14 of 69
		Effective Date	07/05/2018

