5.1.3 Protocol Violations

Protocol violations are major deviations from the procedures outlined in the protocol like for example missed evaluations, incorrect timing of evaluations, non-compliance with study medications and intake of medications not allowed or any non-adherence to the protocol that impacts subject's rights, safety or welfare.

Protocol violations are defined as any deviations that may affect the efficacy outcome or the treatment of the subjects. All potential protocol violations will be discussed and reviewed on a case-by-case basis. A decision will be made as to the effect of the possible violations to determine if it is considered major or minor. The status, major or minor, of each potential protocol violation will be tabulated. A subject may have one or more major protocol violations resulting in the exclusion of that subject from the per protocol analysis set.

Collected Variables: Not applicable

Derived Variables:

- protocol violation category
- type of violation (descriptive free text)
- details of violation (descriptive free text)

Imputations for missing values: Not applicable

Analysis Sets to be used for:	Tables	ITT analysis set
	Listings	ITT analysis set
	Figures	Not applicable

Protocol violations will be summarized by treatment group as follows:

Table 8. Major/Minor Protocol Violations (ITT set) The number of all subjects with at least one major or minor protocol violation, will be presented by treatment group. For all categories of major and minor protocol violations, default frequency tabulation will be presented. Subjects may have more than one major/minor protocol violation.

Subjects data listings will include:

Listing 6. Minor and Major Protocol Violations A by-subject listing of all subjects with their minor and major protocol violations will be presented.

	Form	Form No.	1M-DMST-011-01-A1
	Statistical Analysis Plan	Page	Page 16 of 69
		Effective Date	07/05/2018

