	Statistical Analysis Plan	Page	Page 22 of 69
		Effective Date	07/05/2018

Analysis of Primary Efficacy variable:

Descriptive statistics such as mean \pm standard deviation, median with interquartile range, minimum, maximum and coefficient of variation will be presented for the plasma concentration of coenzyme Q10 at each time point in the entire sample of subjects. 95% confidence interval will be provided as well.

An explorative analysis on gender will be performed showing descriptive statistics for plasma concentration of coenzyme Q10 by gender. The effect of gender will be explored by means of a mixed model for repeated measures with covariates *gender*, time and the interaction term *gender*time*.

Descriptive statistics will be also provided for the plasma concentration of coenzyme Q10 at each time point by treatment group.

Change of plasma concentration versus baseline (i.e. change versus visit 2 values) will be computed for each study visit both for the whole sample and by treatment group.

Change will be computed in the following way:

$$\text{Change (\%)} = \frac{\text{Value at Visit X} - \text{Baseline Value}}{\text{Baseline Value}} \times 100$$

Area under the curve, maximum concentration in the plasma, time of maximum concentration and terminal half-life will be presented descriptively on the original scale.

95% confidence interval will be provided for the means of 100mg OD and 100mg BID for COQUN ORAL FORMULATION for the parameters AUC_t , C_{max} , T_{max} and terminal half-life. A Student t-test for unpaired data will be performed in order to detect differences between the two groups in the pharmacokinetics parameters.

A concentration by time graph will be presented for the multidose phase by treatment group in order to have a graphical visualization of the pharmacokinetics properties over time.

Line graphs will be provided for the concentration of coenzyme Q10 in the whole sample and by gender.

In performing statistical analysis, it is important to assess the statistical outliers. In fact, inclusion or exclusion of outlying subjects may lead to a different conclusion in assessment of differences in bioavailability between two formulations. It is therefore important to identify these outliers and study their effects.

Primary endpoint will be evaluated on the ITT population and analysis will be replied on the PP population. Results obtained on the PP population will be considered as supportive of those obtained on the ITT set.

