Line graphs will be provided for the concentration of coenzyme Q10 in the whole sample and by gender.

In performing statistical analysis, it is important to assess the statistical outliers. In fact, inclusion or exclusion of outlying subjects may lead to a different conclusion in assessment of differences in bioavailability between two formulations. It is therefore important to identify these outliers and study their effects.

Analysis will be evaluated on the ITT population and analysis will be replied on the PP population. Results obtained on the PP population will be considered as supportive of those obtained on the ITT set.

Imputations for missing values: No imputation of missing data will be performed

Analysis Sets to be used for:	Tables	ITT and PP analysis set
	Listings	ITT analysis set
	Figures	ITT and PP analysis set

Plasma concentration of coenzyme Q10 in the single dose phase will be summarized as follows:

Table 25. Plasma Concentration of Q10 in the Single Dose Phase (ITT Analysis Set)

Default summary statistics for plasma concentration of Coenzyme Q10 at each time point will be presented for the ITT analysis set.
This table will be replied on the PP analysis set.

Table 26. Plasma Concentration of Q10 in the Single Dose Phase by gender (ITT Analysis Set)

Default summary statistics per gender for the Plasma concentration of Coenzyme Q10 at each time point will be presented for the ITT analysis set.
This table will be replied on the PP analysis set.

Table 27. Change versus baseline by gender (ITT Analysis Set)

Default summary statistics by gender for the change versus baseline at each time point will be presented for the ITT analysis set.
This table will be replied on the PP analysis set.

	Form	Form No.	1M-DMST-011-01-A1
	Statistical Analysis Plan	Page	Page 29 of 69
		Effective Date	07/05/2018

Table 28.
Pharmacokinetic Parameters in the Single Dose Phase (ITT Analysis Set)

Default summary statistics for each pharmacokinetic parameter will be presented for the ITT analysis set together with confidence intervals at 95% for the means of the pharmacokinetics parameters.
 This table will be replied on the PP analysis set.

Plasma concentration of Q10 will be presented in subject data listings as follows:

Listing 24. Listing of Plasma Concentration of Q10 in the Single Dose Phase

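### One per-protocol flag serves both phases, so a major deviation confined to one phase also removes the subject from the supportive per-protocol analysis of the other

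*Protocol*

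**What the plan says.** Protocol 12.4.3, repeated in SAP 3.1, defines the PP population once, with no reference to phase: "The per protocol population consists of all subjects who meet all inclusion/exclusion criteria and who do not have any major protocol deviation". SAP 5.1.1 turns this into one status per subject: "PP set (subjects must have been randomized and they do not have major deviations". SAP 5.1.3 gives the consequence of a major violation: "A subject may have one or more major protocol violations resulting in the exclusion of that subject from the per protocol analysis set". Its examples of violations are "missed evaluations, incorrect timing of evaluations, non-compliance with study medications and intake of medications not allowed", none of them tied to a phase.

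That one set is used twice. For the multidose outputs (Tables 13-17, Figures 3-5), SAP 5.2.1 says: "Primary endpoint will be evaluated on the ITT population and analysis will be replied on the PP population". For the Day -7 outputs (Tables 25-28, Figures 6-7), SAP 5.2.3 says: "Analysis will be evaluated on the ITT population and analysis will be replied on the PP population". The templates for Table 1, Table 3 and Listing 4 each carry a single PP entry. Neither document defines a phase-specific or PK-evaluable set. Both SAP sections describe PP as supportive of ITT.

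**The concern.** The Day -7 profile is complete 12 hours after the dose. Randomisation follows at V2 (Day 0), and the multidose phase runs to Day 28. Non-compliance in week 3 cannot change a concentration measured on Day -7. Likewise, a mistimed Day -7 sample does not alter the V2-V5 concentrations on which the once-daily and twice-daily groups are compared. Under a single flag, either event, if rated major, excludes the subject from both PP analyses.

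At stake is what the PP repeat can tell the reader. It is there to show whether the ITT result survives removal of compromised data. If PP and ITT differ in one phase, the difference may come wholly from exclusions made for events in the other phase, and the tables would not show this.

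**Working it through.** **Does the text produce the effect?** There are two routes.

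1. *Through a major deviation.* SAP 5.1.3 gives each violation one status, major or minor, and that status feeds the single flag of SAP 5.1.1. A violation relevant to one phase can therefore exclude the subject from both PP analyses or from neither. It cannot exclude from one only.
2. *Through eligibility.* Protocol 12.4.3 and SAP 3.1 also require every inclusion criterion to be met. One criterion in Protocol 8.2 extends the bar on prescribed medication through the study itself. Read literally, a prescription in the 28-day phase fails that criterion and drops a Day -7 profile already completed.

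**How large could it be?** The plan has no figure to reproduce. Protocol 12.3 states that the 24 subjects (12 + 12) do not come from a power calculation, and no deviation rate is given anywhere.

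Assumptions: a major-deviation rate q1 of 0 to 10% on Day -7, a rate q2 of 5 to 30% in the 28-day phase, and independence between the two.

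Formulas, with N = 24:
- one flag: expected PP size 24(1 − q1)(1 − q2), the same for both analyses
- two flags: 24(1 − q1) for single dose, 24(1 − q2) for multidose
- intact Day -7 profiles lost under one flag: 24(1 − q1)q2
- intact multidose subjects lost under one flag: 24·q1(1 − q2)

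| q1 | q2 | One flag | Two flags: single / multi | Intact Day -7 lost | Intact multidose lost |
|---|---|---|---|---|---|
| 0 | 5% | 22.8 | 24 / 22.8 | 1.2 | 0 |
| 0 | 30% | 16.8 | 24 / 16.8 | 7.2 | 0 |
| 5% | 10% | 20.5 | 22.8 / 21.6 | 2.3 | 1.1 |
| 10% | 5% | 20.5 | 21.6 / 22.8 | 1.1 | 2.3 |
| 10% | 20% | 17.3 | 21.6 / 19.2 | 4.3 | 1.9 |
| 10% | 30% | 15.1 | 21.6 / 16.8 | 6.5 | 1.7 |

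Across the grid, 1.1 to 7.2 intact Day -7 profiles are lost on average. The chance of losing at least one is 1 − (1 − p)^24 with p = (1 − q1)q2. It runs from 67% (p = 0.10 subtracted from 1, times 0.05, = 0.045) to over 99% (p = 0.30). On the multidose side the average loss is 0 to 2.3 subjects.

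**Precision.** The half-width of a 95% interval for one mean, in SD units, is t(0.975, n − 1)/√n:
- n = 24: 0.422
- n = 20: 0.468, since 0.468/0.422 ≈ 1.11, about 11% wider

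Four lost profiles out of 24 correspond to q2 = 4/24 ≈ 17% with q1 = 0. At the 90% level of Protocol 12.1 the half-widths are 0.350 and 0.387, again about 11% wider.

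**The case against.** The strongest reply is that exclusion is not automatic. SAP 5.1.3 says "All potential protocol violations will be discussed and reviewed on a case-by-case basis", and only a violation judged major excludes. No rule makes one missed sample or a few missed capsules major. This stands, and it limits how often the problem arises. It does not remove it, because the judgement still yields one rating for one flag. The plan also leaves unclear when the review would happen, since SAP 3.3 states: "No data review has been planned in this study".

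The eligibility route is open to a narrower reading as well. The SAP's inclusion/exclusion section has the criteria answered at screening and checked again before allocation at V2. A later prescription might then never alter the eligibility entry, and would be handled only as a possible violation. In addition, SAP 5.1.1 does not repeat the eligibility condition. The route therefore depends on taking Protocol 8.2 and 12.4.3 literally.

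The consequence is also modest. PP is supportive, ITT keeps every randomised subject, no hypotheses are pre-specified (Protocol 12.6), and the SAP places the single-dose analysis under other variables. All of this stands and bears on priority. It does not make a PP set that mixes the two phases informative.

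**Conclusion.** The structural point holds in both directions and rests on the wording alone: one flag, two phases, and no means of excluding a subject from one PP analysis only. The size is illustrative. The 1.1 to 7.2 lost profiles depend on assumed, independent deviation rates, and the 11% widening depends on an assumed loss of four subjects. The effect is confined to supportive analyses, so this is an inexpensive correction worth making and not a threat to the main results.

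A reader might infer more, and the documents do not support it:
- *That missed capsules or a missed 8-hour sample would necessarily delete data from the other phase.* They would do so only if rated major.
- *That the single-dose PP result is biased because later non-adherence reflects tolerance of the first dose.* Conditioning on later events is real, but nothing in either document links later adherence to the Day -7 dose.
- *That the interval for the difference between the dose groups widens.* Table 17 plans intervals for the group means, a point difference and a p-value. It plans no interval for the difference.

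**What to change.** Amend the SAP before database lock. Assign each major deviation to the phase or phases it affects, and derive two flags, both within the randomised (ITT) set so that each PP set nests in the set it supports:

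- **PP-single-dose:** entry criteria met as assessed up to the 12-hour sample, Day -7 dose taken, and no major deviation affecting the Day -7 profile. Use it for Tables 25-28 and Figures 6-7.
- **PP-multidose:** eligibility criteria met, and no major deviation affecting the multidose phase from the start of wash-out to Day 28. Use it for Tables 13-17 and Figures 3-5. Wash-out belongs here because V2 is the multidose baseline (SAP 4.4).

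Limiting the eligibility check for the first flag to the 12-hour sample matters. Without that limit, the medication criterion that runs through the study would bring the same problem back. Separately, Protocol 8.2 bars prescribed medication during the study while Protocol 9.8 allows medication to treat adverse events. Those passages need to be reconciled.

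Show both flags in Tables 1 and 3, Listing 4 and Figure 2, and add a phase column to Listing 6. Protocol 12.1 lets the SAP explain departures from the planned analysis, so the change can be recorded in SAP section 6, which at present reports none.

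The cost is wording, one extra derived flag, and PP denominators that differ slightly by phase. No new data or subjects are needed, and ITT does not change. A subject who leaves between Day -7 and V2 stays outside both PP sets and ITT, as now.

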12.5 Subgroup Analysis

N.A

12.6 Statistical Hypothesis

The study aims are to explore, compare and describe the data for research purposes; no hypotheses are pre-specified.

12.7 Analysis of Primary Variable

The primary variables are the pharmacokinetic properties:

- Area under the curve (microg/ml x h): ≥ 5
- Cmax: $\geq 0,8$
- Tmax: ≥ 3
- elimination half-life (t 1/2)

At each time point and for each group, descriptive statistics and 90% confidence intervals will be provided. See section **12.1** for details.

Analysis of primary endpoints will be performed on Intention-To-Treat population and Per Protocol population.

12.8 Analysis of Secondary Variables

The secondary variables are the ones regarding safety which will be monitored through vital signs, physical exams, ECGs, clinical laboratory tests and adverse events, as follows:

- Following a single oral dose of 100mg COQUN ORAL FORMULATION
- in 1 month period of daily oral intake of 100mg OD or BID COQUN ORAL FORMULATION

Symptoms and signs like mild insomnia, elevated levels of liver enzymes, rash, nausea, upper abdominal pain, dizziness, sensitivity to light, irritability, headache, heartburn, and fatigue will be closely monitored.

At each time point and for each group, descriptive statistics will be provided. See section **12.9** for details.

12.9 Analysis of Safety Variables

12.9.1 Adverse Events

	Study Title	Bioavailability Study of COQUN ORAL FORMULATION (CoQ10) administered in Healthy Adults (CoQ10-01)		
	Study ID	VF-BAQ10/2018	Sponsor:	VISUFARMA SpA
	Date	March 03, 2018	Vers.	Final

Safety will be monitored through vital signs, physical exams, clinical laboratory tests (hematology) and adverse events including assessment of relationship to the IP.

Analysis of safety will be performed on the safety set.

The recorded adverse events will be coded according to MedDRA. The adverse events will be summarized by treatment, System Organ Class, preferred-term and intensity.

Nature, incidence and intensity, as well as the investigator's and the sponsor's causality assessment will be reported for each treatment-emergent adverse event. Descriptive summary statistics, e.g., with regard to the incidence of symptoms and the causality assessment, will be presented for the period between V1-V5. Furthermore, all non treatment-emergent adverse events during pre-treatment will be reported between the ICF signature and the first IP intake at V1.

12.9.2 Clinical Laboratory

Clinical laboratory data will be presented on an individual basis and will be marked according to the normal ranges provided by the selected central laboratory and corresponding sponsor guidelines, respectively. Descriptive summary statistics will be presented for each variable. In addition, the number of subjects with values outside the normal range and extended normal ranges will be presented.

12.10 Analysis of other Variables

N.A

12.11 Missing Values

No replacement of missing values will be performed.

13 SUBJECT SCREENING

Subjects screened for inclusion irrespective whether they are enrolled or not, have to be documented on the screening log provided by the sponsor and screening visit procedures shall be described in the source document, as well as the reasons for non-inclusion.

The screening/enrolment is finished as soon as the sponsor terminates the screening period of the study for having reached the planned subject number.

14 DATA QUALITY ASSURANCE AND STUDY DOCUMENTATION

All data concerning the study will be documented in the subject's medical records and transferred afterwards in the CRF designed especially for this study; for data clarifications, if necessary, query forms will be used and filed together with the CRF. The CRF will be checked for completeness and plausibility by the monitor together with the clinical investigator.

	Study Title	Bioavailability Study of COQUN ORAL FORMULATION (CoQ10) administered in Healthy Adults (CoQ10-01)		
	Study ID	VF-BAQ10/2018	Sponsor:	VISUFARMA SpA
	Date	March 03, 2018	Vers.	Final

14.1 Monitoring

It is the responsibility of the investigator to assure that the study is conducted in accordance with the protocol and that valid data are entered into the CRF.

The investigator will permit a representative of the sponsor/CRO to monitor the study as frequently as necessary, to determine that data recording, IP handling, and adherence to the Study Protocol are satisfactory. The CRF and all related documents will be reviewed in detail in accordance with the SOPs of the CRO and Good Clinical Practice regulations.

To verify compliance with this Study Protocol, the sponsor will require that the investigator permits the monitor to review those portions of the subject's primary medical records which directly concern this study.

It is the investigator's obligation to ensure that documentation of all relevant data such as medical history/concomitant diseases, date of study enrollment, visit dates, results of examinations, administration of IP, and AEs (incl. clinical relevant abnormal laboratory results, if any) are correctly entered in the subjects' files as well as in the CRF.

The sponsor/the sponsor's delegates will affirm and uphold the principle of the subject's right to protection against the invasion of privacy. Throughout the study and for all analysis, all data will only be identified by the subject number.

